6.3 Analysis of Exploratory Endpoints

6.3.1 Presence of active SARS-CoV-2 infection on at the end-of-treatment visit

Viral RNA assessment will be performed at the end-of-treatment visit. In the case where viral RNA assessment data is unavailable or patient died during the study, that subject will be treated as having a positive viral RNA test result. Fisher exact and/or chi-square test will be used to compare the proportion of subjects who have negative viral RNA test result between two treatment groups.

6.3.2 Incidence, duration, and extent of new oxygen therapy use (re-initiation 24 hours or more after cessation of prior oxygen therapy)

The number and percentage of patients reporting new oxygen therapy use (i.e., mechanical ventilation or supplemental oxygen therapy) as well as types of new oxygen therapy use will be tabulated by treatment groups. The duration of new oxygen therapy use will be calculated from the re-initiation of oxygen therapy use. For subjects with death of any cause or withdrawal of study participation after the re-initiation of oxygen therapy use, the duration of new oxygen therapy use will be imputed with the longest duration observed in the study. The duration of new oxygen therapy use will be presented by descriptive statistics.

6.3.3 Incidence, duration, and extent of new mechanical ventilation use (re-initiation 24 hours or more after cessation of prior mechanical ventilation)

The number and percentage of patients reporting new mechanical ventilation use, and types of new mechanical ventilation use will be tabulated by treatment groups. The duration of new mechanical

^a Values are with respiratory support

^b To convert bilirubin from mg/dL to μmol/L, multiply by 17.1

^c Adrenergic agents administered for at least 1 hour (doses are given in µg/kg/min).

^d For subjects who are intubated, the verbal response is scored as:

^e For subjects who are sedated, use an estimated score for Glasgow Coma Scale (the assumption is 15, if no other factors than sedation affect Glasgow Coma Scale score).

f To convert creatinine from mg/dL to μmol/L, multiply by 88.4

ventilation use will be calculated from the re-initiation of mechanical ventilation use. For subjects with death of any cause or withdrawal of study participation after the re-initiation of mechanical ventilation use, the duration of new mechanical ventilation use will be imputed with the longest duration observed in the study. The duration of new mechanical ventilation use will be presented by descriptive statistics.

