## Table 1:Schedule of Assessments

	Study Day(s) a													
	Part 1 and Part 2 a								Pa	art 2 onl	y a	Part 1 and Part 2 a		
List of activities/assessments	Screening/baseline —7 to 1 b	2	3	4	5	6	7	8-10	11	12-14	15	16-21	EOT and discharge day a,n	Safety follow- up assessment a Up to and including Study Day 51 (+7)
Informed consent b	Х													
Inclusion/exclusion b	Х													
SARS-CoV-2 confirmation c	Х													
Medical history 	Х													
Demographics	Х													
eGFR/ALT	Х													
Serum pregnancy test	Х													
Height/body weight/BMI d	Х													
Randomization (Part 2 only)	Х													
Study drug administration a	Х	Х	Х	Х	Х	Х	Χ	Х	X	X	Х	Х	Х	
Discharge card dispensation e													Х	
SAFETY ASSESSMENTS														
Vital signs f	Х	Х	Х	Х		Х	Χ	Х	X	X	Х	Х	Х	
ECG f	Х	Х	Х	Х		Х	Χ	Х	X	X	Х	Х	Х	
SOFA score g	Х		Х		Х		Χ		X		Х		Х	
Clinical laboratory tests h	Х		Х		Х		Χ		X		Х		Х	
Viral RNA or viral antigen assessment k	Х						Χ				Х		Х	
Radiograph/CT scan (pulmonary consolidation)	Х						Χ						Х	
Concomitant medications and procedures i	Х	Χ	Х	Х		Х	Χ	Х	X	X	Х	X	Х	Х
Infusion site reactions j	Х	Х	Х	Х		Х	Χ	Х	X	X	Х	Х	Х	Х
Adverse events	Х	Х	Х	Х	Х	Х	Χ	Х	X	X	Х	X	Х	Х
PHARMACODYNAMIC AND PHARMACOKINETIC ASSESSMENTS														
PK (APL-9)/PD (complement, coagulation, and inflammation)	X		Х		X		Х		Х		Х		$X^{m}$	

Abbreviations: ABG = arterial blood gas; AE = adverse event; ALT = alanine aminotransferase; ARDS = acute respiratory distress syndrome; BMI = body mass index; CT = computed tomographic; DMC = data monitoring committee; ECG = electrocardiogram; eGFR = estimated glomerular filtration rate; EOT = endof-treatment visit;  $FiO_2$  = fraction of inspired oxygen; GCS = Glasgow Coma Scale; ICU = intensive care unit;  $PaO_2$  = partial pressure of oxygen; PD = pharmacodynamics; PK = pharmacokinetics; SAE = serious adverse event; SARS-CoV-2 = severe acute respiratory syndrome coronavirus 2; SOFA = Sequential Organ Failure Assessment;  $SpO_2$  = peripheral oxygen saturation.

Apellis Pharmaceuticals, Inc

#### APL-9 APL9-COV-201 Protocol Amendment 3

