- i The concomitant procedures include recording the day that the subject was admitted to the ICU (or ICU-type environment), use of ventilatory support, use of oxygen therapy, date of ICU discharge, date of hospital discharge, and survival. The time and date of any changes to concomitant medications and procedures are to be recorded at the days indicated in the schedule of assessments. In case of early hospital discharge, the data is collected via phone interviews.

#### APL-9 APL9-COV-201 Protocol Amendment 3

- j Infusion-related reactions that occur during the administration of the 50-mL loading dose should be treated as follows: For mild infusion-related reactions: The 50-mL bag infusion time should be increased from 10 min to 20-40 min and the reaction should be monitored. Treatment with diphenhydramine may be required. The infusion time of the 250-mL bag should not be increased. For severe or persistent mild infusion-related reactions (instances in which the subject's symptoms do not respond to the increased infusion time), treatment should be discontinued, and the institution's emergency hypersensitivity protocol should be employed. Refer to the procedure for handling infusion-related reactions in Section 9.1.1.
- k Confirmation of SARS-CoV-2 infection for screening may be completed more than 7 days before baseline.
-  Vaccination history should be attempted to be collected as a component of medical history.
- m A PK/PD assessment will be done on the last day of treatment. If EOT and discharge day visit are on different days, a PK/PD sample will be collected on the discharge day as an unscheduled visit.
- n If EOT and day of discharge visit are on different days, perform EOT assessments on the last day of treatment and repeat on the day of discharge as an unscheduled visit. Perform/record vital signs, ECG, concomitant medications/procedures, infusion site reactions, and AEs daily up to and including day of discharge. After EOT, record as unscheduled visits.

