## 11. STUDY ASSESSMENTS AND PROCEDURES

- Day 1 is defined as the day upon which study treatment is first administered.
- The last predose assessments will be considered as baseline assessments.
- Study procedures and their timings are summarized in the SoA (Table 1). Protocol waivers or exemptions are not allowed.
- Significant safety concerns should be discussed with the sponsor immediately upon occurrence or awareness to determine whether the subject should continue or discontinue study participation.
- Adherence to the study design requirements, including those specified in the SoA (Table 1), is essential and required for study conduct.
- All screening evaluations must be completed and reviewed to confirm that potential subjects meet all eligibility criteria. The investigator will maintain a screening log to record details of all subjects screened and to confirm eligibility or record reasons for screening failure, as applicable.
- Procedures conducted as part of the subject's routine clinical management and obtained before signing of the informed consent form (ICF) may be utilized for screening or baseline purposes provided that the procedures met the protocol-specified criteria and were performed within the time frame defined in the SoA (Table 1).
- The study end-of-treatment assessments are to be conducted at the end of treatment or on the day of hospital discharge, whichever occurs later. The posttreatment follow-up assessment, conducted 30 days after the last dose of study drug (with a +7-day window), may be conducted either in the hospital or by telephone so that subjects do not have to be exposed to the hospital environment after hospital discharge.
- Discharged subjects will be provided with emergency study cards that include a list of symptoms associated with infections. The study card also guides subjects with instructions to contact their study physicians or seek emergency medical care in the event they experience any of the listed symptoms.

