6. EFFICACY ANALYSIS

All efficacy analyses will be summarized for each study part. Efficacy data will also be analyzed by treatment group in Part 2. Hypothesis testing will be performed for part 2 between two treatment groups.

Unless otherwise specified, baseline for all efficacy analyses is defined as the last non-missing measurement recorded prior to taking the first dose of study drug.

All CIs will be presented as 2-sided 90% and/or 95% CIs. All statistical tests will be 2-sided hypothesis tests performed at the 10% level of significance.

The primary efficacy analyses will be performed for full analysis set (FAS). The supportive efficacy analyses will be performed for Intent-to-Treat (ITT) set.

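### SAP 6.3.1 lets a later death reverse an observed negative end-of-treatment swab, and compares arms on a swab whose day is neither fixed nor uniquely identified

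*SAP*

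**What the plan says.** The endpoint is exploratory. Protocol 6.2.3 and SAP 2.2.3 both define it as active infection at the end-of-treatment visit. SAP 6.3.1 repeats this: "Viral RNA assessment will be performed at the end-of-treatment visit". Its imputation rule is that if "viral RNA assessment data is unavailable or patient died during the study, that subject will be treated as having a positive viral RNA test result". On the test: "Fisher exact and/or chi-square test will be used to compare the proportion of subjects who have negative viral RNA test result". SAP 6 sets the level: "All statistical tests will be 2-sided hypothesis tests performed at the 10% level of significance".

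Two protocol passages locate the visit differently. Section 11 places the assessments "at the end of treatment or on the day of hospital discharge, whichever occurs later". Table 1 footnote n, for the case where the two days differ, says to "perform EOT assessments on the last day of treatment and repeat on the day of discharge", and labels the repeat an unscheduled visit.

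The treatment end in Part 2 is tied to Day 7 or the approved duration, coming off respiratory support, and discharge (Protocol 7.1, SAP 3.1). The DMC may allow extension up to Day 21, but only for subjects who are still on support at Day 7 and whose oxygenation has improved. Protocol 7.4 ends the study at the follow-up 30 days after the last dose, up to Day 51 with a 7-day window.

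Table 1 also has a row "Viral RNA or viral antigen assessment", marked at screening/baseline, Day 7, Day 15 and end of treatment/discharge.

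**The concern.** The endpoint has a time point, the end-of-treatment visit, and the death rule reaches past it. A subject swabbed negative on the last treatment day who dies three weeks later is analysed as infected at that visit. That replaces an observation with a contrary value because of something that happened afterwards.

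The visit day is itself a post-randomization outcome, so randomization does not balance it. Swab positivity can be expected to fall with time. If treatment changes who qualifies for extension or when subjects are discharged, one arm may be swabbed later and show more negatives with no antiviral effect. Where the last treatment day and discharge day differ, there may be two results, and SAP 6.3.1 does not say which is analysed.

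At stake is the reading of a stated exploratory objective, the effect of APL-9 on active infection. Among the unredacted exploratory endpoints this is the only one with a between-arm test; SAP 6.3.2 and 6.3.3 are descriptive.

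**Working it through.** **What the rule does.** With a swab on the last treatment day, the follow-up is 30 days later, plus up to 7. For last treatment on Day 21, 21 + 30 = Day 51, which matches the protocol's limit. A death anywhere in that interval turns a recorded negative into a positive under the literal wording.

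**Inputs from the documents.** About 60 subjects randomized 1:1, so about 30 per arm; two-sided level 0.10; Fisher exact and/or chi-square test. The documents give no design figure for this endpoint to reproduce. They also give no clearance rate, no death risk and no share of subjects extended, so those are assumptions below, shown as ranges. Rejection probabilities come from exact enumeration of all outcomes with 30 per arm (chi-square uncorrected).

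**Later deaths.** Let q be the true proportion negative at the swab, equal in both arms, and m the proportion who die after it, independent of the result. Then the proportion analysed as negative is q × (1 − m). For q = 0.60 and m = 0.10 versus 0.20: 0.60 × 0.90 = 54% versus 0.60 × 0.80 = 48%, a 6-point difference with no difference in clearance. Over q = 40% to 80%:

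| Deaths after swab | Fisher rejects | Chi-square rejects |
|---|---|---|
| 10% vs 10% | 5.2-5.5% | 9.2-10.3% |
| 10% vs 20% | 6.8-11.0% | 11.2-16.9% |
| 10% vs 30% | 11.0-26.1% | 16.9-35.0% |

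To the extent that some deaths come before the swab, fewer results are overwritten and the effect is smaller.

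**Swab day.** Assume the same constant clearance hazard in both arms, with median time M, so the proportion clear by day t is 1 − 2^(−t/M). Let 50% of one arm and 20% of the other be read late, the rest at Day 7. For M = 10: Day 7 = 38.4%, Day 21 = 76.7%. The arms then show 0.5 × 38.4 + 0.5 × 76.7 = 57.6% and 0.8 × 38.4 + 0.2 × 76.7 = 46.1%, an 11.5-point difference from timing alone. Over M = 7 to 20 days:

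| Reading day | Fisher rejects | Chi-square rejects |
|---|---|---|
| Late readings at Day 14 | 7.8-9.3% | 13.2-14.6% |
| Late readings at Day 21 | 12.5-15.3% | 18.9-22.1% |
| Everyone at Day 7 | 4.8-5.6% | 9.1-10.8% |

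**A real effect.** For true clearance of 70% versus 40%, power is 66.5% (Fisher) and 75.5% (chi-square) with no overwriting. With 10% overwritten in each arm the compared proportions are 63% and 36%, and power falls to 56.9% and 67.0%.

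**Which swab.** Section 11 takes the later of end of treatment and discharge. Footnote n takes the last treatment day and calls the discharge repeat unscheduled. SAP 12.4 prefers a scheduled result to an unscheduled one within a visit window, which leans toward footnote n, but it does not address two end-of-treatment swabs.

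**The case against.** Counting death as failure is a recognised composite choice, and it fits the SAP's handling of deaths elsewhere: SAP 6.2.1, 6.3.2 and 6.3.3 impute the longest observed duration. That stands for deaths before the swab. It does not justify reversing a result already observed for an endpoint fixed at that visit, and any-cause mortality is already a secondary endpoint.

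A reader might infer that the test measures timing and mortality rather than clearance. The documents do not support that. Clearance remains a component, and a real difference is still detected with reduced power. With equal death risk and timing, the test keeps its level.

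The timing scenarios need extended treatment in some subjects, and no document says an extension was approved. Without one, the spread in last treatment days shrinks, though early stopping remains possible and Section 11 can still move the swab to a later discharge day. The timing model also gives extended subjects the same clearance curve as the others, although extension is selective.

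A reader might also conclude that Day 7 should replace end of treatment. That would contradict Protocol 6.2.3 and SAP 2.2.3, drop later clearance, and bring response-dependent timing back if earlier swabs stood in for subjects discharged before Day 7. Day 7 belongs in a supportive analysis.

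**Conclusion.** The concern holds in a limited form. That the rule can reverse an observed negative, and that the swab analysed is not uniquely identified, follow from the text without numerical assumptions. The visit day does depend on clinical course.

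The consequence is conditional. The comparison mixes clearance with swab day, later death and missing results (also scored positive), and misleads only to the extent that these differ between arms. In the moderate scenarios above (10% versus 20% later deaths, or 50% versus 20% read late), chi-square false rejection is about 11-22% against a nominal 10%. Fisher, being conservative, is about 7-15%. These figures rest on assumed clearance, death and extension rates and on independence of death and swab result. The endpoint is exploratory and no decision in the documents depends on it, so this is a worthwhile clarification of minor weight.

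**What to change.** In SAP 6.3.1:

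- Keep every observed end-of-treatment result. Impute positive for death only when it occurs before the end-of-treatment swab.
- State that the last-treatment-day swab is analysed and that the discharge-day repeat is unscheduled, as in footnote n. Reconcile this with Protocol Section 11.
- Add a supportive between-arm comparison at the Day 7 swab already in Table 1, leaving the end-of-treatment endpoint as defined. State how survivors without a Day 7 result are handled, and show their number by arm.

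Separately, Protocol 7.1 ends Part 2 treatment at the latest of several events, while Protocol 10.1 ends it at the DMC-allowed maximum or discharge. These imply different end-of-treatment days and must be reconciled; this review takes no position on which is right.

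The cost is SAP wording, a clarification in Protocol Section 11, and slightly more analysis; no new sample is needed. The downside is that deaths after the swab no longer count as failures in this endpoint, but they remain in the mortality analysis.

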## 8.4. Screening Failures

Sites may initiate screening procedures prior to a subject's diagnosis of respiratory failure or ARDS. Confirmation of SARS-CoV-2 infection may be completed more than 7 days before baseline. All other inclusion and exclusion criteria must be met within –7 days of baseline. Screening failure is defined as the situation of a subject who consents to participate in the clinical study but does not receive study treatment. A minimal set of screening failure information is required to ensure transparent reporting of screening failures to meet the Consolidated Standards of Reporting Trials publishing requirements and to respond to queries from regulatory authorities. Minimal information includes demography, screening failure details, eligibility criteria, and any SAEs.

Subjects may be rescreened with approval from the sponsor.

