## 11.4. SARS-CoV-2 Viral RNA/Viral Antigen Assessment

Presence of SARS-CoV-2 viral RNA or viral antigen will be detected in respiratory specimens (collected using nasopharyngeal or oropharyngeal swabs) with a qualitative nucleic acid amplification test (such as RT-PCR) or viral antigen test or other diagnostic method that is authorized, cleared, or approved by the US Food and Drug Administration (or equivalent local authority) for SARS-CoV-2 viral detection. Serology-based antibody tests do not detect the presence of virus and therefore are not considered diagnostic for active infection and cannot be used for study eligibility screening or for subsequent SARS-CoV-2 assessments.

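### SAP 6.3.1 analyses end-of-treatment infection by viral RNA only, so a permitted antigen-only negative is scored positive if the rule is applied as written

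*SAP*

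**What the plan says.** SAP 6.3.1 names viral RNA and no other assay. A Fisher exact and/or chi-square test serves to "compare the proportion of subjects who have negative viral RNA test result between two treatment groups". The missing-data rule is triggered by "In the case where viral RNA assessment data is unavailable or patient died during the study", in which case "that subject will be treated as having a positive viral RNA test result".

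The endpoint itself is wider. SAP 2.2.3 and protocol 6.2.3 define it by detection of viral RNA or viral antigen, or by another authorised method. Protocol 11.4 describes the assessment as a nucleic acid test "or viral antigen test or other diagnostic method that is authorized, cleared, or approved by" the regulator. The row in protocol Table 1 is "Viral RNA or viral antigen assessment", marked at screening/baseline, Day 7, Day 15 and EOT/discharge.

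On baseline status, protocol 8.4 says "Confirmation of SARS-CoV-2 infection may be completed more than 7 days before baseline", and Table 1 footnotes c and k repeat this. SAP 6.3.1 makes no use of the screening/baseline result, and SAP 5.2 does not list viral status among the baseline characteristics.

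**The concern.** A site may follow the protocol exactly, run an antigen test at end of treatment and record a negative. That subject has no RNA datum. Under 6.3.1 the RNA assessment is then unavailable and the subject enters the comparison as positive, so the rule reverses an observed result. How often this happens depends on each site's choice of assay, which is neither randomised nor a stratification factor (SAP 3.3).

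A second, weaker point concerns Day 1. The qualifying test may be more than 7 days old and no positive swab is required at baseline, so some subjects may already be negative when dosing starts. They count as negatives at end of treatment in either arm and can only dilute the difference.

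What is at stake is the reading of one exploratory endpoint. The primary safety objective is not touched.

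**Working it through.** **Inputs from the documents.** About 30 subjects per arm (SAP 3.2); two-sided tests at the 10% level (SAP 6); Fisher exact and/or chi-square, unadjusted (SAP 6.3.1).

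**Inputs assumed, because the documents do not give them.** Truly negative at end of treatment: 70% on APL-9 and 40% on vehicle. Share with an antigen test only, *a*: 0 to 40%, equal in the arms unless stated. Share already negative on Day 1, *q*: 0 to 30%.

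**The plan's own figure.** No power is stated for the viral endpoint. The only sample-size figures are the chances of seeing at least one SAE, 1 − (1 − p)^30. These reproduce: 26.0%, 70.6%, 88.7% and 95.8% at p = 1%, 4%, 7% and 10%, against the stated 26%, 71%, 89% and above 95%.

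**Antigen-only negatives scored positive.** The scored negative proportion is (1 − *a*) × the true proportion, so the arm difference is multiplied by (1 − *a*). Power is for the exact two-sided Fisher test at 0.10, by full enumeration with 30 per arm.

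| *a* | Scored negative, APL-9 vs vehicle | Difference (points) | Power |
|---|---|---|---|
| 0% | 70% vs 40% | 30 | 67% |
| 10% | 63% vs 36% | 27 | 57% |
| 20% | 56% vs 32% | 24 | 48% |
| 40% | 42% vs 24% | 18 | 33% |

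**False positives.** With 50% truly negative in both arms, the Fisher rejection rate is 5.2% at *a* = 0 and 5.2% at *a* = 20% in both arms. It rises to 12.7%, above the nominal 10%, only when antigen-only use is made unequal, 10% in one arm and 30% in the other.

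**Day 1 negatives, taken alone (*a* = 0).** If they stay negative, the proportion in each arm is *q* + (1 − *q*)*p*, where *p* is 70% or 40% among Day 1 positives. The last two columns restrict to Day 1 positives: first with every subject swabbed in the Day −7 to 1 window, then with some lacking a swab (20%, 20% and 30% for the three rows).

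| *q* | Difference, all subjects (points) | Power, all subjects (30 per arm) | Power, Day 1 positives, all swabbed | Power, Day 1 positives, some not swabbed |
|---|---|---|---|---|
| 10% | 27 | 58% | 63% (27 per arm) | 52% (22 per arm) |
| 20% | 24 | 51% | 59% (24 per arm) | 48% (19 per arm) |
| 30% | 21 | 44% | 48% (21 per arm) | 36% (15 per arm) |

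Restriction gains 4 to 8 points if every subject has a swab in the window, and loses power in the last column.

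**The case against.** **Viral RNA may be shorthand.** The heading of 6.3.1 names the same endpoint that SAP 2.2.3 defines broadly, and the schedule has a single combined row. A sensible programmer might count antigen results. This is plausible and limits the point to the rule as written. It does not remove it. SAP 1 says that its analyses supersede the protocol's, SAP 14.2 records that 6.3.1 was already reworded for clarity, and SAP 14.1 declares no change from the protocol. A narrowing to RNA is thus neither disclosed nor apparently intended, yet the text still says RNA only.

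**The endpoint is presence at end of treatment, not clearance.** This stands. Comparing all randomised, treated subjects answers the stated question, and randomisation balances Day 1 negatives in expectation. They cost power and cause no bias. Making Day 1 positives the lead comparison would change the question. It could also drop subjects, because footnote k can be read as letting an older test stand in for the screening swab.

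**A reader might infer that the rule could produce a false effect of APL-9.** The documents do not support that. Equal misclassification only attenuates. The 12.7% rejection rate needs antigen-only use to differ between blinded arms, and nothing in the plan supplies a mechanism for it. Assay choice that varies by site is not choice that varies by arm, although chance imbalance is possible with 30 per arm.

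**Conclusion.** The point holds as a mismatch between SAP 6.3.1 and the endpoint it analyses: the stated rule turns a permitted, observed antigen-only negative into a positive. With equal use in the arms, the consequence is attenuation. On the assumed 70% versus 40%, the 30-point difference falls to 27, 24 or 18 points at antigen-only shares of 10%, 20% or 40%, with the power losses tabulated above, and there is no loss if every subject has an RNA result. Ignoring Day 1 status is a possible further loss of power and is not an error in the lead comparison.

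The sizes rest on assumed shares and negative rates. Misclassification in the actual data is not demonstrated, and neither is bias between arms. One exploratory endpoint is affected, so this is a minor point, worth correcting because it is easy to correct.

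**What to change.** In SAP 6.3.1:

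- Replace viral RNA with viral RNA, viral antigen or other authorised SARS-CoV-2 test.
- Count an observed negative by any permitted method as negative.
- Apply the positive imputation for missing data only when no result of any kind exists. Leave the rule for deaths unchanged.
- Tabulate assay type at baseline and end of treatment by arm, so that any imbalance is visible.
- Keep all subjects as the lead comparison. Add, as supportive, either an analysis in subjects with a positive swab at screening/baseline (Day −7 to 1) or one adjusted for Day 1 status, and state how many subjects lack a baseline swab.

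The cost is SAP wording, one table and one supportive analysis. No new assessment is needed, since the swabs are already scheduled. The supportive analysis will have fewer subjects if it is restricted, which is why the count without a baseline swab should be reported. The change should be made before unblinding.
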